6.0 Treatment Plan

**THE USE OF LIPOSOMAL BUPIVACAINE FOR PAIN CONTROL FOLLOWING
MASTECTOMY AND IMMEDIATE IMPLANT BASED BREAST RECONSTRUCTION**
Wake Forest Baptist Comprehensive Cancer Center
CCCWU # 99517

	Preoperative Visit	Day of Surgery	Upon discharge home	1 st 12hr post discharge	2 nd 12hr post discharge	3 rd 12hr post discharge	4 th 12hr post discharge	1 week postop	3 weeks postop	5 weeks postop
Life Orientation Test-Revised	X									
PROMIS- Depression	X									
PROMIS- Anxiety	X									
Pain Catastrophizing Scale	X									
Baseline Pain Assessment	X									
Enrollment and informed consent	X									
Receive surgical site infiltration of Exparel or bupivacaine		X								
Q 12 hour pain scores				X	X	X	X			
Patent diary of narcotic use and pain rating			X					X		
Disability assessments								X	X	X
Pain assessments								X	X	X

6.1 Study-Related Activities

Patient involvement in the study will be initiated in the plastic surgery clinic. Eligible subjects will be identified prior to surgery. Potential subjects will be contacted either by phone or during their clinic visit, informed consent will be obtained and a 30-minute preoperative assessment will be performed. Patients will be informed that if they are expected to undergo an axillary lymph node dissection at the time of surgery then they will be excluded from the study. Patients who are undergoing sentinel lymph node biopsies will be included in the study, but if their nodes are positive and there is an intraoperative decision to pursue axillary lymph node dissection they will subsequently be excluded from the study. Also, we will record demographic and history information, including existing pain elsewhere, and administer questionnaire-based measures of psychological state, physical function, and baseline pain (Table 1, Appendix F). Questionnaire responses will be entered via the cancer center REDCap data entry form. From these questionnaires, we will place each participant on a dimensional continuum that describes their general cognitive style. We will use multidimensional scaling (MDS) to force catastrophizing and optimism as 2 ends of this continuum.

Table 1. Preoperative Questionnaires

Life Orientation Test-Revised (LOT-R)

PROMIS- Depression

PROMIS- Anxiety

Pain Catastrophizing Scale (PCS)

**THE USE OF LIPOSOMAL BUPIVACAINE FOR PAIN CONTROL FOLLOWING
MASTECTOMY AND IMMEDIATE IMPLANT BASED BREAST RECONSTRUCTION**

Wake Forest Baptist Comprehensive Cancer Center
CCCWU # 99517

[figure not shown]
These two constructs describe cognitive styles that are strongly inversely associated with each other; MDS will provide the optimal weights to best order individuals on this latent scale. Studies have examined the interplay of these constructs with other psychological concepts such as acceptance, pain-related disability and psychosocial adjustment and have found that both are reliably associated with the positive and negative aspects of the adjustment to pain.

The research coordinator will then assign the patients a study number. On the day of surgery, each patient will be randomized to be in one of the following two groups for perioperative local anesthetic infiltration:

1. Local infiltration of bupivacaine
2. Local infiltration of liposomal bupivacaine

The study will be double blinded to both patients and providers including plastic and general surgeons involved in their operative care. We will enroll our patients in pharmacy randomization program, in which the pharmacy will deliver the appropriate medication per assigned group.

To monitor our primary outcomes, patients will be asked to rate their pain level on a visual analog scale (Table 2, Appendix Z) with activity every 12-hours after surgery during their post-procedure stay. The activity for which they will rate their pain will be the arm movements associated with eating. In the hospital, their visual analog scores will be provided to each patient in person by their nurse every 12 hours. Subject's pain scores will continue to be recorded every 12 hours via a phone call from a study team member for the first 48 hours after discharge. Additionally, while in the hospital, the amount of narcotics used will be recorded and converted into morphine equivalents.

Upon discharge, patients will be given a sheet to record their pain level and the amount of narcotics & benzodiazepines used (Appendix K). Both the amount of narcotics & benzodiazepines and the pain level are to be reported at the time of taking any narcotics & benzodiazepines. Patients will follow up with our clinic at 1 week, 3 weeks, and 5 weeks postoperatively. At week 1 patients will bring in their medication and pain diary, and fill out a pain assessment (Appendix G) in addition to a questionnaire assessing breast cancer surgery

THE USE OF LIPOSOMAL BUPIVACAINE FOR PAIN CONTROL FOLLOWING MASTECTOMY AND IMMEDIATE IMPLANT BASED BREAST RECONSTRUCTION

Wake Forest Baptist Comprehensive Cancer Center
CCCWU # 99517

disability (Appendix H)²³. During subsequent appointments made at 3 and 5 weeks postoperatively, they will be assessed and receive the pain assessment and breast cancer surgery disability assessments as well. When tissue expansion is initiated will be determined by the primary surgeon, but we will track the dates of the initiation of expansion as this will impact pain scores within the electronic medical record.

Secondary outcomes including length of hospital stay, adverse opioid effects and re-admission rate will be tracked by their electronic medical record. Upon reviewing the questionnaires, if a subject is determined to have high levels of depression, our team will make them aware of the resources available in the psychiatry department and a contact number will be provided to them.

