5.2.2 Morphine equivalents used within the first month postoperatively

THE USE OF LIPOSOMAL BUPIVACAINE FOR PAIN CONTROL FOLLOWING MASTECTOMY AND IMMEDIATE IMPLANT BASED BREAST RECONSTRUCTION

Wake Forest Baptist Comprehensive Cancer Center
CCCWU # 99517

- 5.2.2.1 The number of doses of oral narcotics (hydrocodone-acetaminophen 1 tablet) for patients with immediate tissue expander reconstruction without other measure of pain control has been 4.2 at 24 hours and 4.0 at 48 hours¹⁷. This is approximately 3.3 morphine equivalents
- 5.2.2.2 We would expect the patients treated with liposomal bupivacaine to use an average of 2.5 intravenous morphine equivalents at the 48-hour point and decreased morphine equivalents in the liposomal bupivacaine over the first postoperative month.
- 5.2.3 Length of stay for hospitalization after mastectomy and breast reconstruction
 - 5.2.3.1 Length of stay for patients undergoing mastectomy and immediate reconstruction has been shown to be 41-47 hours on average²¹
 - 5.2.3.2 We believe liposomal bupivacaine will shorten this time to 36 hours±12 in the liposomal bupivacaine group, but not in the bupivacaine groups.
- 5.2.4 Readmission rates to the hospital within 2 months after mastectomy and breast reconstruction
 - 5.2.4.1 Patients who underwent tissue expander breast reconstruction have a readmission rate of approximately 4.34%²². We anticipate a readmission rate of approximately 2% Patients will be informed that if they are expected to undergo an axillary lymph node dissection at the time of surgery then they will be excluded from the study. Patients who are undergoing sentinel lymph node biopsies will be included in the study, but if their nodes are positive and there is an intraoperative decision to pursue axillary lymph node dissection they will subsequently be excluded from the study.
- 5.2.5 Frequency of postoperative opioid related adverse effects within the first week of surgery. This includes nausea, vomiting, pruritus, allergy, respiratory depression.
 - 5.2.5.1 After immediate breast reconstruction with implants, patients receiving bupivacaine had a 40% incidence of nausea and vomiting. Those not receiving a local anesthetic had a 75% incidence of nausea and vomiting¹⁷
 - 5.2.5.2 We predict a 30% incidence of opioid related adverse events in our liposomal bupivacaine group
- 5.2.6 Trajectory of postoperative recovery from pain within the first 2 months

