Appendix G – Pain Assessment

Subject Number: _____ DATE: ____/____/____ TIME: ____:____ AM/PM

1 - Rate the intensity of your worst pain in the past 24 hours related to your operated breast/chest.

0 1 2 3 4 5 6 7 8 9 10

2 – Please rate the intensity of breast pain that you have while eating.

0 1 2 3 4 5 6 7 8 9 10 Cannot Do

3 – If it has been one month or longer since your surgery please complete the following question:

Please lift your arms to the sides of your body at a 90-degree angle. Rate the intensity of breast pain that you have during this activity.

0 1 2 3 4 5 6 7 8 9 10 Cannot Do

Not Applicable

4 - Rate your level of disability in the past 24 hours to do normal daily activities.

0 1 2 3 4 5 6 7 8 9 10

5 - Rate your level of disability in the past 24 hours to do activities you enjoy.

0 1 2 3 4 5 6 7 8 9 10

6 - Did you take prescription pain pills in the past 24 hours? YES NO

If yes please circle the medication below and complete question 5b

THE USE OF LIPOSOMAL BUPIVACAINE FOR PAIN CONTROL FOLLOWING
MASTECTOMY AND BREAST RECONSTRUCTION

Wake Forest Baptist Comprehensive Cancer Center
CCCWU # TBD

6a1 – Oxycodone

6a2 - Hydromorphone (Dilaudid)

6a3 - Hydrocodone + acetaminophen (Vicodin, Norco)

6a4 Valium

6b - In the last 24 hours, how many prescription pills have you taken for your pain?

**THE USE OF LIPOSOMAL BUPIVACAINE FOR PAIN CONTROL FOLLOWING
MASTECTOMY AND BREAST RECONSTRUCTION**

Wake Forest Baptist Comprehensive Cancer Center
CCCWU # TBD

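### First-week opioid adverse effects are to be taken from the medical record, and nothing in the plan asks patients about them after discharge, when most of the week still lies ahead

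*Combined protocol and SAP*

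**What the plan says.** Objective 2.2.5 and outcome 5.2.5 set a one-week window: "Frequency of postoperative opioid related adverse effects within the first week of surgery. This includes nausea, vomiting, pruritus, allergy, respiratory depression". For the source of these data, Section 6.1 states: "Secondary outcomes including length of hospital stay, adverse opioid effects and re-admission rate will be tracked by their electronic medical record".

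On length of stay, 5.2.3.1 cites a figure that "has been shown to be 41-47 hours on average", and 5.2.3.2 adds: "We believe liposomal bupivacaine will shorten this time to 36 hours±12 in the liposomal bupivacaine group, but not in the bupivacaine groups".

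After discharge the planned contacts are:

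- **Phone calls (6.1).** Pain scores are "recorded every 12 hours via a phone call from a study team member for the first 48 hours after discharge". No other item is listed for these calls.
- **Diary (Appendix K).** Date, drug and dose, number of pills, time and pain rating.
- **Week-1 visit (6.1, Appendices G and H).** Pain, disability and pill use. The nearest item to an opioid effect in Appendix G is "Did you take prescription pain pills in the past 24 hours", which concerns intake and not symptoms.
- **Schedule table (6.0).** It has no row for adverse effects.

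Separately, 7.4 says that all adverse events are recorded and managed in WISER, Section 9.0 lists WISER as the system for adverse effects, and Appendix E is a log. None of these says how or when a patient is asked.

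**The concern.** Nausea, vomiting and itching at home usually reach a chart only if the patient reports them. A first-week endpoint drawn from the chart, with no prompt after discharge, will tend to record the hospital stay well and the rest of the week poorly.

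Two things follow. The reported incidence would understate first-week experience in both arms, even if stays are equal. And the length of the well-observed period depends on length of stay, which the trial itself expects treatment to change. An arm sent home earlier could show fewer recorded events with no true difference. Symptoms that nobody asked about cannot be recovered at analysis.

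**Working it through.** **The plan's own figure.** Section 10.2.5 gives a detectable difference of 31 points from a 60% rate with 45 per group, two-sided alpha 0.05, 80% power and Fisher's exact test. Exact enumeration for 60% versus 29% with 45 per group gives power 0.790, so the figure reproduces to within about a point. Sections 10.1.1 and 10.3, however, set 25 per arm. At that size the same contrast has power 0.536, and about 41 points are needed for 80%.

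**Share of the week in hospital.** The week is 168 h.

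- 36/168 = 21%, leaving 132 h (79%) after discharge.
- 41/168 = 24%, leaving 127 h (76%).
- 47/168 = 28%, leaving 121 h (72%).

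**How far the calls reach.** They run for 48 h from discharge: 36 + 48 = 84 h after surgery, against 41 + 48 = 89 h to 47 + 48 = 95 h. Contact by phone therefore also ends earlier in the arm with the shorter stay.

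**Size of the tilt when there is no true effect.** From the documents:

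- first-week incidence p = 50% (10.2.5), applied to both arms;
- stay of 36 h on liposomal bupivacaine (5.2.3.2);
- stay of 41-47 h on bupivacaine, which is the cited average (5.2.3.1) read with the statement that only the liposomal arm shortens.

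Assumptions, because the documents give neither:

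- capture is complete in hospital and equals q after discharge;
- onset times have distribution F over the 168 h, either uniform or front-loaded (truncated exponential with mean m).

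The recorded rate for a stay of L hours is p × [F(L) + q × (1 − F(L))]. The spurious difference is p × (1 − q) × [F(L on bupivacaine) − F(36)]. For uniform onset F(t) = t/168; otherwise F(t) = (1 − exp(−t/m)) / (1 − exp(−168/m)).

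With no home capture (q = 0):

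| Onset | Recorded at 36 h | Recorded at 41-47 h | Difference (points) |
|---|---|---|---|
| Uniform | 10.7% | 12.2-14.0% | 1.5-3.3 |
| Mean 48 h | 27.2% | 29.6-32.2% | 2.4-5.0 |
| Mean 24 h | 38.9% | 41.0-43.0% | 2.1-4.1 |
| Mean 12 h | 47.5% | 48.4-49.0% | 0.9-1.5 |

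For example, uniform onset gives 0.5 × 36/168 = 10.7% and 0.5 × 47/168 = 14.0%. With q = 0.5 every difference halves, so the largest is 2.5 points. With q = 1 it is zero.

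The same table shows the under-count. A true 50% is recorded as anything from 10.7% to 49.0% when nothing is captured at home.

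**The case against.** The strongest reply is that the medical record is not the sole route. Section 7.4 and Section 9.0 provide for adverse events in WISER, Appendix E is a log, and 6.3 has supportive treatments, with antiemetics among the examples, entered on flow sheets with reasons and dates. The study team speaks to patients every 12 h for 48 h after discharge and sees them at one week, the end of the window. The record does not close at discharge either, since 6.1 uses it for readmission, which runs to two months. All of this stands. A reader might infer that the record is the only source, or that the days at home are unobserved; the documents support neither. They do support the narrower statement that the symptoms are not systematically asked about after discharge. A storage system and a log do not say who asks what and when, and committee reporting under Appendix D covers only unexpected grade 4 and all grade 5 events.

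A reader might also infer a larger artefact. If 40% or 50% of patients have an event within 41-47 h at a constant rate, stopping at 36 h removes 3.9-7.6 or 4.4-8.8 points. But that rate carried to 168 h implies 1 − 0.60^(168/47) = 84% to 1 − 0.60^(168/41) = 88%, or 92-94% on the 50% version. The plan expects 50% (10.2.5), or 30% in the liposomal arm (5.2.5.2), so those figures do not fit.

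Nor should the artefact be set against a supposed predicted fall from 40% to 30%. The 40% is nausea and vomiting in a cited study (5.2.5.1), and the 30% is all opioid-related events in the liposomal arm. The plan does not state that difference.

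Finally, the shorter stay is only hypothesised, nausea may itself delay discharge, and 10.2.5 concedes that the outcome is not powered. These points stand too. They make the tilt conditional and its size illustrative, but they do not remove the under-count.

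**Conclusion.** The point holds as one about ascertainment. Following the plan as written, first-week opioid adverse effects are likely to be under-counted in both arms, because 72-79% of the window falls after the expected discharge and nothing prompts the patient for these symptoms.

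A tilt towards liposomal bupivacaine follows only if the stay really is shorter in that arm and capture is poorer at home. Its size is then roughly 0-5 points. This assumes 50% true incidence in both arms, average stays of 36 h and 41-47 h, stay unrelated to the event itself, and the onset and capture patterns shown. That is small against a detectable difference of 31 points at 45 per group, or about 41 points at 25 per arm, so a falsely significant result is not the main worry. The worry is a first-week incidence, and an estimated difference, that cannot be taken at face value. The change is worth making because it is cheap now and impossible later.

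**What to change.** In 6.1, add a fixed yes/no checklist of the 5.2.5 symptoms that patients can report (nausea, vomiting, itching, allergic reaction). Ask it of every patient at the existing week-1 visit, covering the time since surgery. Name it in 10.2.5 as the primary source. Its window is the same in both arms whatever the discharge time, which neither the chart nor the calls can offer. Add a row to the schedule in 6.0 and a field in REDCap.

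Optionally, ask the same items at the existing 12-hourly assessments and calls as supporting data. Because the calls are timed from discharge, analyse these over a window fixed from surgery.

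Keep the medical record for respiratory depression, and reconcile 6.1 (medical record) with Section 9.0 (WISER) so that each component has one stated source.

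The cost is a few tick-boxes on existing contacts, with no new visit. There are two drawbacks. Solicited rates will be higher in both arms than the rates cited in 5.2.5.1, so they should not be compared directly. And the week-1 question depends on recall, which the optional 12-hourly items would partly offset.

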6.2 Treatment Administration

Patients assigned to the local infiltration with bupivacaine group will receive a total 60 ml of 0.25% bupivacaine with 30 ml delivered to each breast. Patients assigned to the local infiltration of liposomal bupivacaine will receive a total of 20 ml liposomal bupivacaine (266 mg) with 10 ml of 0.25% bupivacaine and 30 ml of 0.9% sodium chloride. These injections will occur at the end of the mastectomy and prior to the insertion of the tissue expander implant. The local anesthetic will be injected into the chest wall and skin flaps. Attending physicians and resident physicians will receive prior instruction regarding correct placement of the local anesthetic so that it will be consistently placed in the same locations with similar volume distribution. After this intraoperative injection, patients will not receive any more doses of local anesthetics.

6.3 General Concomitant Medication and Supportive Care Guidelines

This local anesthetic will get delivered at the time of surgery in an opaque syringe. Standardized anesthetic criteria will be applied to all patients enrolled in the study. Pre-operatively, all patients will receive multi-modal therapy, such as acetaminophen, celecoxib, and gabapentin or pregabalin unless contraindicated. Intraoperatively, patients will only receive short acting fentanyl for analgesia. Intraoperative ketamine and dexamethasone will be avoided. A notification will populate in EPIC once the patient is linked to the study in WISER to notify the anesthesia provider. Postoperative non-opioid medications will supplement as needed opioid mediations for analgesic management.

Patients will receive full supportive care as medically necessary, including transfusions of blood and blood products, antibiotics, antiemetics, etc. Medications considered necessary for the patient's well-being may be given as long as they are considered safe in the postoperative period and clinically indicated. The reason(s) for treatment, dosage, and dates of treatment will be recorded on the flow sheets.

6.4 Duration of Follow Up

Patients will be seen at one week, three weeks and five weeks postoperatively at which time they will receive pain and disability assessments.

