2.2 Secondary Objective(s)

- 2.2.1 To evaluate the effect of liposomal bupivacaine on cumulative pain control within the first 48 hours after mastectomy and breast reconstruction
- 2.2.2 To evaluate the effect of liposomal bupivacaine on the amount of postoperative narcotic use after mastectomy and breast reconstruction for the first month after surgery
- 2.2.3 To evaluate the effect of liposomal bupivacaine on length of hospital stay after mastectomy and breast reconstruction
- 2.2.4 To evaluate the effect of liposomal bupivacaine on hospital readmission rates a within 2 months after mastectomy and breast reconstruction
- 2.2.5 To evaluate the effect of liposomal bupivacaine on the occurrence of opioid adverse effects within the first week of surgery after mastectomy and breast reconstruction
- 2.2.6 To evaluate the effect of liposomal bupivacaine on the trajectory of postoperative pain control within 2 months after mastectomy and breast reconstruction

THE USE OF LIPOSOMAL BUPIVACAINE FOR PAIN CONTROL FOLLOWING
MASTECTOMY AND IMMEDIATE IMPLANT BASED BREAST RECONSTRUCTION

Wake Forest Baptist Comprehensive Cancer Center
CCCWU # 99517

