rate, 2-sided alpha of 0.05 and 80% power, we could detect a difference of 31% between the 2 arms using a Fisher's Exact Test

- 10.2.6 For trajectory of postoperative recovery from pain, Growth curve analysis of pain intensity with movement scores over the first two months, using an initial log (time) model and a Bayesian change point analysis
 - 10.2.6.1 Groups will be compared for intercept and slope of the trajectory of pain intensity up to the first change point
 - 10.2.6.2 For the entire population, the impact of the optimism-catastrophizing continuum and other predictive factors for intercept and slope will be explored

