10.5 Estimated Study Length

Estimated study length will be approximately 2 years. This will include patient enrollment through the 5 week patient follow up period.

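### The pain trajectory is defined over two months, but the last scheduled pain score is at week 5

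*Combined protocol and SAP*

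**What the plan says.** **Two-month window.** Objective 2.2.6 is "To evaluate the effect of liposomal bupivacaine on the trajectory of postoperative pain control within 2 months after mastectomy and breast reconstruction". Outcome 5.2.6 repeats the horizon: "Trajectory of postoperative recovery from pain within the first 2 months". Outcome 5.2.6.1 and section 10.2.6 specify the method: "Growth curve analysis of pain intensity with movement scores over the first two months", with a log(time) model first and then a Bayesian change point analysis. Both add that the arms are compared on intercept and slope only as far as the first change point.

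**Five-week data collection.** Section 6.4, which sets the duration of follow-up, reads: "Patients will be seen at one week, three weeks and five weeks postoperatively at which time they will receive pain and disability assessments". The schedule table and section 6.1 give the same three visits. Section 6.1 has the medication and pain diary returned at week 1.

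**Readmission.** Objective 2.2.4 concerns "hospital readmission rates a within 2 months after mastectomy and breast reconstruction", and outcome 5.2.4 is "Readmission rates to the hospital within 2 months after mastectomy and breast reconstruction". Section 6.1 takes readmissions from the electronic medical record and gives no date at which that review stops. Section 10.5 estimates the study length at about two years and adds: "This will include patient enrollment through the 5 week patient follow up period".

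**The concern.** The analysis window is longer than the period in which pain is measured, and this holds for every patient. A team following the plan to the letter would have to draw the last part of the curve from the model alone, or else shorten the window after the data are in. Neither is a good position for a prespecified objective.

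Two features of the plan make extrapolation past week 5 unsafe. Section 6.1 says that the start of tissue expansion affects pain scores and leaves its timing to the surgeon. A curve fitted to week 5 cannot show expansion-related pain that begins later. The method also looks for change points, and one that falls after the last score cannot be found.

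The readmission outcome shares the two-month horizon and sits beside a study length described by the 5-week follow-up. This raises the question whether the last patients are looked up for the full window.

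**Working it through.** **Inputs**

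- Window: 2 months, taken as 61 days (assumption; range 56–62).
- Last scheduled pain score: week 5 = day 35 (schedule table, 6.1, 6.4).
- Accrual: 25 patients a year to a total of 50 (10.4), assumed uniform.
- Readmission rates: 4.34% from a prior study and about 2% anticipated (5.2.4, 10.2.4). The plan does not assign the 2% to an arm, so both rates are applied to all 50 patients.

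**1. The plan's own study length.** Accrual time plus follow-up is 50/25 + 35/365.25 = 2.00 + 0.10 = 2.10 years. This agrees with the two years or so stated in 10.5.

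**2. Is there any pain score after week 5?** The schedule table, 6.1 and 6.4 contain none. The diary comes back at week 1 and records pain only when a narcotic or benzodiazepine is taken. One item in Appendix G applies from one month after surgery, but the week-5 visit already meets that condition, so the item does not imply a later visit.

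**3. Unobserved part of the trajectory window**

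- Linear time: 61 − 35 = 26 days, and 26/61 = 43%. With 56 days it is 21/56 = 38%; with 62 days it is 27/62 = 44%.
- Log(time), starting at 12 hours: 1 − ln(35/0.5)/ln(61/0.5) = 1 − 4.25/4.80 = about 12%.
- Log(time), starting at day 1: 1 − ln(35)/ln(61) = 1 − 3.56/4.11 = about 14%.

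**4. Readmission if record review ends at the last 5-week visit**

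- Patients with a shortened window: 25 × 26/365.25 = about 1.8 of 50.
- Each loses on average half of the 26 days: 1.78 × 13 = about 23 patient-days of 50 × 61 = 3,050, or 0.8%.
- Expected readmissions: 50 × 0.02 = 1.0 to 50 × 0.0434 = 2.2.
- Expected missed events under a uniform hazard (assumption): 1.0 × 0.0076 = 0.01 to 2.17 × 0.0076 = 0.02.

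**5. Readmission if record review stopped at week 5 for every patient.** 1.0 × 26/61 = 0.4 to 2.17 × 26/61 = 0.9 events missed.

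**6. Study length with record review to 2 months for all.** 2.00 + 61/365.25 = 2.17 years. This is about 26 days longer and still rounds to two years.

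**The case against.** The strongest reply is that the treatment comparison does not need data to day 61. Intercept and slope are compared only as far as the first change point. If that point falls before day 35, the comparison uses observed scores throughout. This stands, and it limits the damage to the description of the curve after week 5 and to any change point located there.

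A second reply is that 43% exaggerates the gap, because the plan's first model is in log(time), where the unobserved share is about 12–14%. This stands as a statement about the model's scale. It does not create scores after week 5, and pain that rises with later tissue expansion need not follow a log(time) curve.

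A third reply is that a two-month limit may be only an outer bound. The objective could bear that reading, but 10.2.6 sets the analysis itself over the first two months.

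On readmission, the reply is largely right. The record does not depend on visits and no week-5 stop is stated. Section 10.5 is an estimated length and sets no data cut-off, and 10.2.4 already says the study is not powered for this outcome. A reader might infer that the 2-month readmission rate will be materially too low, since one missed event among 50 patients moves it by 1/50 = 2 percentage points. The documents do not support that: if only late enrolees are cut short, 0.01–0.02 missed events are expected.

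**Conclusion.** The mismatch is real and affects every patient. The plan states a two-month pain trajectory, and its schedule observes the first 35 of about 61 days. About 26 days have no scheduled score. A curve over that stretch would be extrapolation, and a change point there would go undetected.

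A reader might go further and infer that the trajectory cannot be studied at all, or that the between-arm comparison is invalid. The documents do not support either. The first five weeks are observed, and the comparison stands if the first change point falls before day 35. The documents give no basis for saying where it will fall. The primary outcome, confined to the first 48 hours, is untouched.

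Readmission is a minor matter of wording. About 1.8 of 50 patients are affected on the strict reading of 10.5, with 0.01–0.02 events missed. This would rise to 0.4–0.9 events only if review stopped at week 5 for everyone, which the text neither states nor rules out. These figures assume uniform accrual, a uniform hazard and a 61-day window.

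**What to change.** 1. Replace the two-month window with five weeks in 2.2.6, 5.2.6, 5.2.6.1 and 10.2.6. This costs only wording; the downside is that the trajectory claim covers a shorter period. If the longer window matters to the sponsor, the alternative is to schedule a 2-month pain score for every patient, at the cost of one more contact each.
2. Keep readmission at 2 months, and state in 6.4 and 10.5 that record review runs to 2 months after each patient's surgery. This costs a record lookup per patient and about 26 days at the end of the study (2.17 against 2.10 years). It leaves the stated estimate of about two years intact. A lookup in the trial's own record would not by itself find admissions to other hospitals, before or after week 5.
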